8.3.1	Investigator Reporting, Notifying Mayo IRB.....	21
8.3.2	Investigator Reporting: Notifying the FDA.....	21
8.4	UNBLINDING PROCEDURES (BREAKING THE BLIND) (AS NECESSARY IF THE STUDY IS BLINDED).....	22
8.5	STOPPING RULES.....	23
8.6	MEDICAL MONITORING	23
8.6.1	Internal Data and Safety Monitoring Board	Error! Bookmark not defined.
8.6.2	Independent Data and Safety Monitoring Board	Error! Bookmark not defined.
9	DATA HANDLING AND RECORD KEEPING.....	23
9.1	CONFIDENTIALITY.....	23
9.2	SOURCE DOCUMENTS.....	23
9.3	CASE REPORT FORMS	24
9.4	RECORDS RETENTION	24
10	STUDY MONITORING, AUDITING, AND INSPECTING	25
10.1	STUDY MONITORING PLAN	25
10.2	AUDITING AND INSPECTING	25
11	ETHICAL CONSIDERATIONS	25
12	STUDY FINANCES	26
12.1	FUNDING SOURCE	26
12.2	CONFLICT OF INTEREST.....	26
12.3	SUBJECT STIPENDS OR PAYMENTS	ERROR! BOOKMARK NOT DEFINED.
13	PUBLICATION PLAN	26
14	REFERENCES	26
15	ATTACHMENTS	ERROR! BOOKMARK NOT DEFINED.

LIST OF ABBREVIATIONS

AE	Adverse Event/Adverse Experience
CFR	Code of Federal Regulations
CRF	Case Report Form
DSMB	Data and Safety Monitoring Board
FDA	Food and Drug Administration
GCP	Good Clinical Practice
HIPAA	Health Insurance Portability and Accountability Act
IDE	Investigational Device Exemption
IRB	Institutional Review Board
PHI	Protected Health Information
PI	Principal Investigator
SAE	Serious Adverse Event/Serious Adverse Experience
SOP	Standard Operating Procedure
UADE	Unanticipated Adverse Device Effect
ECM	Extracellular matrix
EMR	Endoscopic mucosal resection
EGD	Esophagogastroduodenoscopy
BE	Barrett's esophagus

Study Summary

Title	A Randomized Study of the Use of Biologic Scaffolds in Constructive Healing Following Endoscopic Resection
Running Title	Biologic Scaffold Study
IRB Protocol Number	16-006909
Phase	Device Feasibility trial
Methodology	Randomized study
Overall Study Duration	1 year
Subject Participation Duration	12-16 weeks
Objectives	This study is being done to assess the efficacy of ECM products in promoting constructive healing as determined by the ability of the resection site to lift during follow-up.
Number of Subjects	20
Diagnosis and Main Inclusion Criteria	18 and older Male or female Able to provide consent Impending endoscopy that may require initial EMR evaluation of esophageal lesions
Study Device	The Acell MatriStem Surgical Matrix will cover the defect site following mucosal resection using endoscopy clips or X-tac
Duration of Exposure	The device will remain attached to the esophagus and integrate with native tissue over time
Reference therapy	There is no reference treatment for comparison
Statistical Methodology	Univariate descriptive statistics and frequency distributions will be calculated, as appropriate for all variables

1 Introduction

This document is a protocol for a human research study. This study will be carried out in accordance with the procedures described in this protocol, applicable United States government regulations and Mayo Clinic policies and procedures.

1.1 Background

The relatively recent introduction of endoscopic resection techniques (endoscopic mucosal resection [EMR] and endoscopic submucosal dissection [ESD]) have enabled endoscopists to excise larger amounts of tissue for accurate staging, and often curative treatment of early esophageal adenocarcinoma. These techniques have largely supplanted esophagectomy for small esophageal cancers which carries significant risks of morbidity and mortality.

One limitation of endoscopic resection, however, is the risk of esophageal stricture formation at the site of resection as a result of the inflammatory healing process that ensues after deep mucosal injury. The esophagus has limited regenerative ability and the default response is volume replacement of the defect with fibrosis.¹ Esophageal stricture can significantly impact a patient's quality of life and often requires treatment via multiple endoscopies for sequential pneumatic dilations, which carry risk of perforation. It has been reported that the risk of stricture formation is directly proportional to the size of the resection defect. Patients with mucosal defects greater than 75% of the esophageal circumference carry a significantly greater risk of stricture formation², and in patients with full circumferential resection the risk may be as high as 88%.^{3,4} Hence, extensive endoscopic resection typically give endoscopists pause. However, this risk of stricture is often justified by the need to excise the lesions en bloc to ensure accurate determination of depth of invasion and also to ensure the complete removal of the lesion.

Various interventions have been described in an effort to prevent stricture formation, including intralesional and systemic steroids, preventative balloon dilation, and prophylactic covered stent, but results are conflicting.⁵ Currently, most endoscopists limit EMR to anticipated defects of 2 cm in diameter or 50% esophageal circumference in an effort to prevent stricture formation.

1.2 Investigational Device

Extracellular matrix (ECM) products such as MatriStem® Surgical Matrix produced by Acell (Columbia, MD)are approved by the US Food and Drug Administration (FDA) to aid in the healing of wounds like those created by EMR. ECM are composed of collagen and natural proteins that provide a re-absorbable scaffold for tissue remodeling have been investigated in preclinical as well as clinical pilot studies and found to facilitate constructive healing following EMR, meaning formation of site-specific functional tissue. Meanwhile, the inflammatory pathway that leads to stricture formation is diverted.

1.3 Preclinical Data

ECM are the result of minimally processing (i.e., decellularizing) biological tissue (e.g., porcine bladder), during which antigenic cellular components are removed while important proteins (e.g., glycosaminoglycans) and an ultrastructure consisting of collagen, fibronectin and basement membrane are preserved.^{1, 6} These components retain their bioactivity in the host, and provide an environment that promotes cell adhesion and proliferation.⁷ ECM scaffold degradation begins to occur rapidly after placement,^{8, 9} reducing the potential for a chronic inflammatory process or foreign body reaction (as described with synthetic biomaterials¹⁰), and releasing cryptic peptides, including various cytokines and growth factors such as vascular endothelial growth factor and basic fibroblast growth.¹¹ These peptides have been shown to exert chemotactic and mitogenic effects on stem and progenitor cells *in vitro* that contribute to the constructive remodeling process.¹²⁻¹⁴ ECM biologic scaffolds made of porcine-derived small intestinal submucosa have been successfully implanted without a keratonocyte layer in animal models. They were effective in reducing esophageal stricture after EMR, while facilitating constructive nonstenotic healing response with formation of all layers of the esophageal wall in a preclinical dog model.¹⁵

1.4 Clinical Data to Date

Observations on the use of ECM in the human esophagus have been reported in several series. Scaffolds from porcine urinary bladder were used to treat five BE patients with high-grade dysplasia/ esophageal adenocarcinoma and long-segment BE (8 to 13cm) following ESD.⁸ The scaffold was applied using a temporary stent that was removed within 9-17 days, allowing scaffold integration with the underlying muscular wall of the esophagus. Complete epithelialization and formation of a new submucosal layer was appreciated during follow-up. All patients required transient postoperative dilation for mild stricture formation in areas not covered by ECM, but were able to then tolerate a normal diet without recurrence of disease during 4-24 month follow-up. No other significant complications were reported. ECM scaffold degradation was noted to occur *in vivo* rapidly without any evidence of residual xenogeneic tissue. Using a similar approach, three additional patients were subjected to endoscopic, circumferential *en bloc* resection of Barrett's with HGD, followed by fundoplication.¹⁶ One patient with incomplete ECM coverage developed an easily dilated stricture, whereas the remaining 2 patients who had complete ECM coverage did not. To date, no randomized clinical trials exist comparing the use of ECM in humans following EMR vs. the current standard of care (i.e., observation).

1.5 Study Rationale and Risk Analysis (Risks to Benefits Ratio)

1.5.1 Study Rationale

Data for alternative strategies to prevent stricture formation remain equivocal. The application of ECM, however, appears promising based on preclinical and clinical data, and ECM are FDA approved for use in wound healing. No randomized clinical trials exist.

As an initial step towards assessing the utility of ECM in stricture prevention, we seek to assess the role of ECM in promoting constructive healing following endoscopic resection of esophageal lesions. This will be determined by the ability of a lesion to “lift” with saline injection during routine endoscopic follow-up. The importance of lift was first reported by Uno et al. in colonic lesions.¹⁷ Inability to lift with fluid injection is suggestive of submucosal tumor invasion, but a false-positive nonlift sign may occur after biopsy as a result of the ensuing inflammatory healing process. We hypothesize that the use of ECM in patients undergoing EMR will mitigate this inflammatory process and promote a more constructive model of healing with reformation of the esophageal wall layers as evidenced by a lift sign. Patients receiving ECM will be compared to patients undergoing EMR without application of ECM.

Data from this study may be used to support larger studies investigating the role of ECM in preventing stricture formation in patients undergoing more extensive endoscopic resections via EMR or ESD.

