3.4 Primary Safety Endpoints

Primary safety endpoints include overall survival, incidence of all serious adverse events including unanticipated adverse device effects, incidence of technical and device failures and malfunctions, and quality of life as measured by the above dysphagia questionnaires.

4 Subject Selection, Enrollment and Withdrawal

Patients will be recruited from the Barrett's Esophagus clinic where patients with Barrett's esophagus, esophageal cancer, and/or esophageal nodules are referred for consideration of endoscopic evaluation and management. Patients with advanced esophageal cancer are typically not referred as they warrant chemoradiotherapy or palliative care, and are not candidates for endoscopic management. Thus, this clinic presents a selective population to screen from, and one we anticipate will be able to provide the proposed number of subjects for this study. It is estimated 75-100 patients with esophageal lesions undergoing EMR will be screened to ultimately meet study enrollment goals.

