7.1 Sample Size Determination

A power analysis was performed for this two independent sample study with a dichotomous endpoint (presence of a saline lift during follow-up EGD). We assume 20% of patients receiving standard of care and no ECM will have a submucosal lift vs. 80% of patients receiving ECM will have submucosal lift. Using a power of 0.8, and alpha of 0.05, this equates to a sample size of 10 for each group for a total of 20 subjects.

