7.2 Statistical Methods

Descriptive Statistics

Univariate descriptive statistics and frequency distributions will be calculated, as appropriate for all variables. Baseline values for demographic, clinical, and outcome variables (primary and secondary) will be tabulated for the treatment groups. These analyses will help identify potential confounding variables to be used as covariates in sensitivity analyses. Distributions across subgroups used in randomization will be compared to assess whether the randomization was successful in equalizing distributions of these prognostic variables across treatment groups. Putative prognostic variables that will be investigated through these descriptive analyses include variables such as presence of submucosal lift, esophageal caliber, need for esophageal dilation, and score on the Mayo Dysphagia Questionnaire.

Handling of Missing Data

Given the small number of patients and minimal follow-up time we do not anticipate missing data.

Primary Hypothesis: To assess the efficacy of ECM products in promoting constructive healing as determined by the ability of the resection site to lift with saline injection during follow-up.

A student unpaired t-test will be performed to compare the incidence of successful lift in the area of prior EMR among ECM and non-ECM groups.

Secondary Hypothesis: Secondary endpoints include efficacy of ECM in preventing symptomatic esophageal stricture formation requiring dilation, preventing dysphagia as determined by questionnaires, and mitigating formation of post-resection scarring as determined by blinded comparison of pre- and post-resection images (taken using white-light endoscopy and electron chromoendoscopy).

Dysphagia questionnaire: student paired t-test will compare the pre and post treatment scores between both groups.

Esophageal diameter: student paired t-test will compare the pre and post treatment sizes between groups.

Interim Analysis

As this is a small pilot study, we will not perform an interim analysis. Any serious adverse events will prompt immediate reevaluation of study methods.

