7.3 Subject Population(s) for Analysis

All-completed population: Only subjects who completed ALL study related procedures and follow-up will be included (Per Protocol) maybe adjusted to subjects who completed the majority of the study visits and procedures. Patients lost to follow-up will be accounted for during calculation of the attrition rate.

8 Safety and Adverse Events

All adverse events occurring during the study, including those not meeting the criteria of an Unanticipated Adverse Device Effect (UADE) will be recorded on the appropriate case report form. Records of these events will be maintained and reports submitted to the FDA and IRB according to the regulatory requirements. Expected clinical adverse events and nonsignificant (not serious) clinical adverse events will not be reported. Expected clinical adverse events and anticipated adverse device effects are those listed in Section 1.5.2.

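### No section says lift is analysed by assigned arm, so an ECM-assigned patient whose patch could not be placed is either dropped or has no defined group

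*Combined protocol and SAP*

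**What the plan says.** - **Rationale (1.5.1).** "Patients receiving ECM will be compared to patients undergoing EMR without application of ECM". The wording is by receipt and application.
- **Sample size (7.1).** The planning rates are also stated by treatment received: "We assume 20% of patients receiving standard of care and no ECM will have a submucosal lift", against "80% of patients receiving ECM will have submucosal lift".
- **Primary analysis (7.2).** The test will "compare the incidence of successful lift in the area of prior EMR among ECM and non-ECM groups". It does not say whether the groups are those assigned or those received.
- **Analysis population (7.3).** "Only subjects who completed ALL study related procedures and follow-up will be included (Per Protocol"). The same sentence allows this to be relaxed to subjects who completed most of the visits and procedures.
- **Randomization (1.6, 3.1, 5.2, 6.2).** The arms are formed by randomization, using envelopes opened during the procedure just after resection (5.2). ECM is then attached to the surrounding tissue (5.3).
- **Failed placement.** Section 3.4 lists "incidence of technical and device failures and malfunctions" as a safety endpoint. Section 5.4 excludes patients lost to follow-up or sent for surgery from the primary objective and does not mention failed placement. Section 4.4.1 withdraws patients with adverse events related to applying ECM.

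No section mentions intention-to-treat or analysis as randomized. None says how an ECM-assigned patient without a placed patch enters the lift analysis.

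**The concern.** Assignment comes before a placement attempt that can fail. Randomization protects the comparison only if patients are counted in the arm the envelope gave. If a patient's group or inclusion depends on whether the patch was fixed, it depends on something that happens after randomization, and in the ECM arm only. Control patients with equally awkward defects are never put to that test, so they stay in the control group.

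Section 5.7 ties defect size and number of resections to post-resection scarring. If those features also make placement harder, the unplaced patients are the ones least likely to lift. Leaving them out of the ECM group raises its lift rate. Adding them to the comparator also lowers the comparator's rate. With 10 patients per arm, one or two such patients matter.

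**Working it through.** **1. The plan's own figure.** The inputs are in 7.1: 20% and 80% lift, "Using a power of 0.8, and alpha of 0.05". Taking alpha as two-sided (not stated), with the pooled-variance formula and no continuity correction:

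n = [1.960·√(2·0.5·0.5) + 0.842·√(0.8·0.2 + 0.2·0.8)]² / 0.6² = (1.386 + 0.476)² / 0.36 = 9.6, so 10 per group.

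This reproduces "sample size of 10 for each group for a total of 20 subjects". Power at 10 per group is 0.817 by the normal approximation. By exact enumeration of the plan's t-test on 0/1 data it is 0.805. The sample size is not in question here.

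**2. Bias when ECM has no effect.** Let h be the share of hard defects, a the lift rate in hard defects and b the rate in the others. Assume placement fails in every hard defect and in no other. The overall rate is p0 = h·a + (1−h)·b. The expected ECM-minus-control difference is:

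- as assigned: p0 − p0 = 0
- unplaced patients dropped: b − p0
- by receipt, unplaced patients added to control: b − (p0 + h·a)/(1 + h)

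The documents give no values for h, a or b, so these are assumptions. The rows with 20% control lift are set to match 7.1.

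| h | a | b | Control lift p0 | Dropped | By receipt |
|---|---|---|---|---|---|
| 0.20 | 0.10 | 0.225 | 0.20 | 0.225 − 0.20 = 0.025 | 0.225 − 0.22/1.2 = 0.042 |
| 0.10 | 0.10 | 0.211 | 0.20 | 0.211 − 0.20 = 0.011 | 0.211 − 0.21/1.1 = 0.020 |
| 0.20 | 0.10 | 0.40 | 0.34 | 0.40 − 0.34 = 0.06 | 0.40 − 0.36/1.2 = 0.10 |
| 0.10 | 0.10 | 0.40 | 0.37 | 0.40 − 0.37 = 0.03 | 0.40 − 0.38/1.1 = 0.055 |
| 0.30 | 0.10 | 0.40 | 0.31 | 0.40 − 0.31 = 0.09 | 0.40 − 0.34/1.3 = 0.138 |

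If a = b (failed placements no harder than the rest), every difference is zero.

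**3. False-positive rate.** This uses the two-sided t-test at 0.05, 10+10 randomized and h = 20%, averaged over the random number of unplaced patients.

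- Control lift 34%: about 8% by receipt, 6% if dropped, 4% as assigned.
- Control lift 20%: between 5% and 6% by receipt, about 5% if dropped, about 3% as assigned.

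**4. What analysis as assigned costs.** Use the planned 80% and 20%, with k of 10 ECM-assigned patients unplaced and lifting at the control rate. ECM-arm lift is [(10−k)·0.80 + k·0.20]/10.

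| k | ECM-arm lift | Difference | Exact t-test power |
|---|---|---|---|
| 0 | 0.80 | 0.60 | 0.805 |
| 1 | 0.74 | 0.54 | 0.71 |
| 2 | 0.68 | 0.48 | 0.59 |
| 3 | 0.62 | 0.42 | 0.46 |

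**The case against.** A reader might infer from 1.5.1 that the plan moves unplaced patients into the control group. The documents do not say so. That sentence closes a rationale section and describes two treatments; it is not a rule for classifying deviations. Section 7.1 states planning assumptions and classifies nobody. Section 7.2 is neutral, and where it checks whether randomization balanced prognostic variables across treatment groups, the groups are plainly the randomized arms. Sections 1.6, 3.1, 5.2 and 6.2 all describe randomized arms. Under 7.3 a patient who did not receive the assigned procedure is more naturally dropped, and 4.4.1 withdraws the patient if the failure came with an application-related adverse event. All of this stands.

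It is equally right that the plan gives no failure rate and does not say that failure is commoner in hard defects. Section 3.4 is a general list of safety endpoints. Under 5.1 a sheet size is chosen to cover each defect. Section 5.7 links size and number of resections to scarring, not to failed placement. A 34% control lift is also well above the plan's 20%, and the higher figure enlarges the bias.

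What remains is the gap itself. Dropping the patient also breaks the randomized comparison, with a smaller bias in the same direction. The relaxed option in 7.3 could keep an unplaced patient who returns and has the saline injection. That patient then needs a group, and the only text that would settle it is worded by receipt.

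**Conclusion.** The point holds as an omission with a foreseeable consequence. The plan never commits the primary lift comparison to the assigned arm, and the wording it does have leads to dropping an unplaced ECM patient or leaves that patient's group undefined. It does not hold as a claim that the plan counts such patients as non-ECM, or that it expects placement to fail in the harder defects.

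If failed placements are the harder defects, both handlings favour ECM. With 20% hard defects, all unplaced, and 10% lift in them, the spurious gain is about 4 points by receipt and 2 to 3 points if dropped at the plan's 20% control lift, and about 10 and 6 points at 34%. At the plan's own control rate the effect on the false-positive rate is modest. If no placement fails, or failures are unrelated to prognosis, there is no bias. The change is still worth making because it is cheap and must be settled before outcomes are known.

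**What to change.** In 7.2, and in matching terms in 1.5.1, state that the primary lift comparison is between patients randomized to ECM and patients randomized to standard of care, whether or not ECM was placed. In 7.3, replace the completer population for the primary analysis with this one, state that a failed placement is not a reason for exclusion, and remove the open-ended relaxation. Changing 7.2 alone would not be enough, because 7.3 could still drop the patient. Report by-receipt and per-protocol results as supporting tables; these also serve a reader who wants to know how ECM performs once placed. Record placement success on the case report form.

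The cost is a few sentences and a diluted estimate if placements fail: with one failure in ten, 74% instead of 80% lift and t-test power of about 0.71 instead of 0.80. No clinical procedure changes. The wording does not supply a lift result for patients who never have the follow-up injection; that is a separate missing-data question.

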1.5.2 Anticipated Risks and Benefits

The study adds minimal risks to procedures that patients are already scheduled to undergo (EMR). A potential risk of ECM is injury during application to the resection site. We propose the use of endoscopic clips or X-tac to carefully attach each corner of the square ECM material to healthy esophageal tissue surrounding the defect site. This will be carried out by an endoscopist with expertise in esophageal disease and endoscopic therapy. The potential benefit of this includes mitigation of the ensuing inflammatory process. Patients undergoing endoscopic resection return for routine endoscopic follow-up in 8-12 weeks. Injection with saline at this time is safe and will be performed by an experienced endoscopist. Saline is typically resorbed by the tissue within minutes of injection.

1.6 Anticipated Duration of the Clinical Investigation

Screening and enrollment will be performed at the time of consent for their endoscopy and anticipated resection. In eligible patients randomized to ECM placement, the endoscopy will require an additional 5-10 minutes for application of ECM. Follow-up will occur per standard of care in all patients undergoing EMR, that is endoscopy in 8-12 weeks or sooner for patient symptoms (e.g., dysphagia).

2 Study Objectives

